5.1.1. POLARx™ and POLARx™ FIT Cryoablation Catheters (Cryoablation Catheter)

The Cryoablation Catheter is a component of the Boston Scientific Cardiac Cryoablation System (“Cryoablation System”) and is a single use, flexible, over-the-wire balloon catheter used to ablate cardiac tissue. The Cryoablation Catheter is used in conjunction with the Console

to induce thermal injury and endocardial tissue necrosis when the balloon is in contact with cardiac tissue and reaches cryoablation temperatures created by a refrigerant injected from the Console into the balloon segment of the POLARx™. The Cryoablation catheter connects to the Console with a Cryo-Cable (for N₂O delivery and removal) and an Extension Cable (for electrical connection via the Interconnection Box). The Cryoablation catheter is designed to be used as a circular mapping catheter deployed within the guidewire lumen during ablation procedures.

The POLARx™ FIT Cryoablation Catheters are additional models (Short Tip and Long Tip) of the POLARx™ cryoablation balloon catheters that are part of the POLARx™ cryoablation system. The POLARx™ FIT catheter is identical to the predicate POLARx™ catheter with the exception that it can be inflated to a larger balloon diameter of 31 mm.

During an electrophysiology (EP) ablation procedure, the Cryoablation Catheter (including the Cryo Mapping Catheter) is inserted through the Cryo Steerable Sheath (POLARSHEATH™) into the venous system, directed into the LA and towards the ostium of the target PV. Once positioning that occludes the PV has been verified, refrigerant is delivered through the Cryo-Cable to the injection coil, which directs the flow of refrigerant toward the interior distal surface of the balloon. This results in a cooled region at the balloon tissue interface, which adheres to the endocardial surface. The low temperature and pressure gradient allows the balloon to thermally create transmural, circumferential tissue necrosis (lesions) and interrupt electrical conduction.

The Cryoablation Catheter is comprised of the following major components, distal to proximal:

- Atraumatic tip
- Double layer balloon system
- Guide wire lumen
- Internal balloon thermocouple
- Injection coil and manifold for delivery of the refrigerant; liquid nitrous oxide (N₂O)
- Catheter shaft; to retrieve the expanded N₂O gas
- Catheter handle
- Distal handle connections

Figure 1: Cryoablation Catheter Distal Tip

Figure 2: Cryoablation Catheter Handle

Table 5.1-2: POLARx™ Cryoablation Catheter Specifications

Balloon diameter	28 mm
Nominal Distal Tip Length M004CRBS2000 (Short tip)	5 mm
M004CRBS2100 (Long tip)	12 mm
Shaft diameter	0.164 in /12.5 F
Working length	99 cm

Table 5.1-2: POLARx™ FIT Cryoablation Catheter Specifications

Inflated Balloon diameter	28/31 mm
Nominal Distal Tip Length M004CRBS2010 (Short tip)	5 mm
M004CRBS2110 (Long tip)	12 mm
Shaft diameter	0.167 in /12.7 F
Working length	99 cm

5.1.2. POLARMAP™ Mapping Catheter (Cryo Mapping Catheter)

The Cryo Mapping Catheter is a single-use, sterile, multi-electrode, diagnostic catheter designed to map cardiac signals during ablation procedures. The catheter is provided in a 20 mm diameter with 8 evenly spaced radiopaque electrodes. The proximal end of the handle contains an electrical connection that integrates with EP lab recording systems. Once deployed through the central guidewire lumen of the Cryoablation Catheter and into the PV, a circular shape is established such that the electrodes contact the endocardial surface. This allows for

recording and interrogation of electrical conduction between the LA and the pulmonary veins. The Cryo Mapping Catheter also allows for delivery of pacing stimuli used in the interpretation of PVI.

Figure 3: Mapping Catheter Assembly

[figure not shown]

Figure 4: Cryo Mapping Catheter with Electrode Arrangements

Table 5.1-3: Cryo Mapping Catheter Specifications

Catheter Model Number	Catheter Diameter	Evenly Spaced Electrodes
M004CRBS7200	20 mm	8

5.1.3. POLARSHEATH™ Steerable Sheath (Cryo Steerable Sheath)

The Cryo Steerable Sheath is a single use, disposable, steerable percutaneous introducer sheath designed for additional maneuverability of standard catheters that are advanced through the sheath and into cardiac chambers. It is comprised of a composite structured single lumen shaft, an ergonomic handle to provide torque and active deflection, and a hemostasis valve to allow safe introduction, withdrawal, and swapping of catheters and wires while preventing air ingress and minimizing blood loss. A side-port is integrated to allow continuous drip infusion, injection through the center lumen, flushing, aspiration, blood sampling and pressure monitoring.

As a component of the Cryoablation System, the Cryo Steerable Sheath is intended to facilitate the placement of diagnostic and/or therapeutic intracardiac devices during percutaneous catheter ablation procedures. The device is indicated for left-sided cardiac procedures via a transseptal approach.

Table 5.1-4: Cryo Steerable Sheath Specifications

Inner diameter	0.165 in / 13.2 F
Outer diameter	0.208 in / 16.0 F
Working length	68 cm
Total length	82 cm
Dilator working length	85 cm
Reach at 90°	4.6 cm
Guidewire compatibility	0.035 in

5.1.4. SMARTFREEZE™ Cryo Console (Console)

The Console is a device that uses N₂O provided from a refillable cylinder to safely pressurize (inflate) and cool the Cryoablation Catheter to cryogenic ablative temperatures. The Console houses the electrical components and software/firmware needed to perform cryoablation procedures. It controls the delivery, recovery, and disposal of N₂O (cryoablation refrigerant) safely and efficiently. The Console user interface provides a means for initiating and ceasing refrigerant delivery. Once the command is received from the console, N₂O is delivered as a chilled liquid to the Cryoablation Catheter for a programmable time duration. The user interface also displays key information allowing the operator to focus attention on critical tasks and speed up the overall procedure.

**Figure 5: Cryo Console**

Integration between the Cryoablation Catheter and the Console includes monitoring catheter as well as console functionality, aided by a number of components such as: power cords, extension cables, inter connection box, foot switch, diaphragm movement sensor, esophageal temperature monitor, scavenging hose, wrench and nitrous oxide tanks.

5.1.5. Diaphragm Movement Sensor

The DMS is a patch device placed on the patient just below the costal cartilage on the right side and used to monitor a phrenic nerve pacing response. It is connected to the ICB sending data to be displayed on the user interface of the Console. By integrating the information into the Cryo Console, the user can be informed when the measured pacing response is lower than a pre-determined value set by the physician.

Phrenic nerve monitoring is a known and essential component in determining safety during a cryoablation procedure. The current SOC technique which is used to monitor for phrenic nerve palsy is to have the physician place his/her hand on the subject's abdomen and assess the subject's diaphragmatic movement during the period within the procedure that requires the physician's full attention (when ablation is occurring).

It has been reported with cryoablation balloon technology that the incidence of permanent phrenic nerve injury occurs in up to 0.4% of the cases (10) of patients undergoing a cryoablation procedure. The physician subjectively decides when injury may be occurring

based on the change in diaphragmatic movement during respiration. The physician suspends ablation if there is a significant reduction in diaphragmatic movement. This is a manual and physician dependent technique where the incidence of occurrence is related to experience in the cryoablation procedure.

An accelerometer in the DMS detects any reduction of diaphragmatic movement indicating phrenic nerve impact, thus helping to reduce procedure related adverse events and potentially improve procedural safety. The DMS is connected to the ICB of the Cryo-Console and sends data to be displayed on the Cryo-Console's user interface (see Figure 6 below).

[figure not shown]

Figure 6: Diaphragm Movement Sensor (DMS) Display

By integrating the information into the Console, the physician can be informed when the measured pacing response falls below a pre-set value. The pre-determined value is programmed by the physician. The value is displayed as a percentage; with the first physical excursion establishing the baseline at 100%. The measurement display changes from “Blue” to “Red” if the value falls below the physician’s programmed pre-set value (see Figure 6 above).

The DMS is designed to be used as an adjunct accessory to continually evaluate diaphragm movement during ablation; as a reminder alert to augment the established clinical practice described above for phrenic nerve assessment. The DMS is not a substitute for physician SOC practice of phrenic nerve assessment during a cryoablation; i.e. physician palpation of the diaphragm, or attentive medical practice.

5.1.6. Esophageal Temperature Monitoring Sensor (ETS)

Esophageal temperature monitoring is a frequently used technique, especially when there is an anatomical concern related to the proximity of the esophagus to the inferior PVs and posterior wall of the LA. The esophageal ulceration is generally reversible, with a reported incidence of 17% of patients (10).

This feature integrates the detection of the esophageal temperature and provides a reminder alert to the physician if the esophageal temperature goes below a physician pre-set value. The measured esophageal temperature turns the measurement display from “Blue” to “Red” if the temperature probe falls below a physician pre-set value. This feature potentially reduces adverse events such as esophageal ulcerations and fistulas. This is a optional safety alert system to the measurement systems used today although the alert is now displayed on the Console.

[figure not shown]

Figure 7: Esophagus Temperature Sensor (ETS) Display

As noted below, the ICB is designed to receive information from other proprietary devices such as an esophageal temperature probe. When connected, the esophageal temperature probe provides monitoring and alert data to the console for display. Esophageal temperature probes are widely available in stand-alone measurement systems and used as such within the EP lab.

The Esophageal Temperature Sensor Cable enables the connection of a commercially available 400 series temperature probe to be connected to the Console.

5.1.7. Other Cryoablation System Components

5.1.7.1. Inter Connection Box (ICB)

The ICB interfaces the Cryoablation Catheter with the Console. It receives the Catheter monitoring signals, DMS data, as well as information from other proprietary devices such as an esophageal temperature probe, a tip pressure sensor and various other safety systems. The ICB then transmits this information to the Console for display and user analysis.

5.1.7.2. Console Foot Switch

The Console Foot Switch interfaces with the Console and allows the user to inflate the Cryoablation Catheter, start and stop flow of N₂O (cryoablation) as well as deflate the Cryoablation Catheter at the conclusion of the ablation.

5.1.7.3. Console Scavenging Hose

The Console Scavenging Hose is a flexible N₂O exhaust line that connects to the hospital gas scavenging system and allows removal of N₂O gas.

5.1.7.4. Cryo Cable

The Cryo Cable is a sterile, single-use cable that provides the connectivity between the Cryoablation Catheter to the Console to support the delivery of liquid refrigerant and the evacuation of remaining N₂O gas.

5.1.7.5. Cryoablation Catheter Electrical Cable

The Cryoablation Catheter Electrical Cable is a sterile, single-use cable that provides the connectivity between the Cryoablation Catheter and the Console ICB.

5.1.7.6. Cryo Mapping Catheter EP Electrical Cables

The EP Electrical Cable is a sterile, single-use accessory for the Cryo Mapping Catheter and is designed to interface (connect) the Cryo Mapping Catheter with EP recording systems.

6. Study Objectives and Endpoints

6.1. *Study Objective*

The study objective is to collect real-world clinical data on safety, effectiveness and procedural success of Boston Scientific Cardiac Cryoablation System (POLARx™ System) when used to perform PVI in the ablation treatment of De Novo AF.

6.2. Study Endpoints

6.2.1. Primary Safety Endpoint

The primary safety endpoint will be evaluated by the safety event free rate at 12 months post-index procedure.

Primary safety events will consist of a composite of the following procedure-related and device-related adverse events.

Acute primary safety endpoint events, events occurring up to 7 days post-index procedure or hospital discharge, whichever is later, include:

- Death
- Myocardial infarction (MI)
- Gastroparesis / injury to vagus nerve
- Transient ischemic attack (TIA)
- Stroke / Cerebrovascular accident (CVA)
- Thromboembolism / Air embolism*
- Cardiac tamponade / perforation
- Pneumothorax
- Serious vascular access complications**
- Pulmonary edema / heart failure
- AV block not attributable to medication effect or vasovagal reaction

* Thromboembolic or air embolic events collected in the study refer to any occlusion of blood vessel(s) that results in clinical symptoms.

** Defined as prolongation of hospitalization, requirement of surgical intervention or blood transfusion.

Chronic primary safety endpoint events, events occurring through 12 months post-index procedure, include:

- Atrial esophageal fistula
- Significant PV stenosis ($\geq 70\%$ reduction of diameter of the PV from baseline*** **OR** presented by patient's symptoms at 12-Month follow-up and requiring intervention)
- Symptomatic pericardial effusion
- Persistent phrenic nerve injury****

*** Recommended to use the same imaging method as baseline.

**** A non-recovered phrenic nerve injury at 12 months post-index procedure will count as a chronic primary endpoint. The study will collect information on phrenic nerve palsy observed before the end of the index procedure and, in case it occurred, will track information for potential recovery during the study visits.

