6.2.4. Additional Endpoints

Additional endpoints and analyses include, but are not limited to:

- Procedure times: LA dwell time*, total ablation time, number of cryo applications per vein, time to thaw, total fluoroscopy time and total procedure time;
- TTI per ablation application, if available;
- Freedom from recurrence of individual types of AF, or new AFLs or ATs between Days 91 and 12-Month follow-up;
- Analysis of additional ablation techniques performed as there is foreseen CTI and roof line ablation performed with other catheters outside PVI;
- Analysis of different anaesthesia techniques (General anaesthesia with or without intubation versus sedation);
- Freedom from AF recurrence in subjects with anatomical variants of PV such as, but not limited to, common ostia, additional pulmonary vein or early branching;
- Freedom from primary effectiveness failure evaluated in subgroups of subjects (termination of AAD versus continuation of AAD after blanking period);
- For subjects undergoing 3D mapping with the Boston Scientific Rhythmia Mapping System and performing a post-procedural map, map information will be collected to determine lesion locations;
- The percentage of subjects that undergo repeat ablation during the course of the clinical follow-up;
- More than one repeat procedure during the blanking period (within 90 days post-index procedure);
- Changes in the quality of life measures (AFEQT and EQ-5D-5L) between baseline and 12 months follow up;
- The percentage of subjects experiencing device-related adverse events;
- Comparison of procedural and therapy success between POLAR ICE (NCT04250714) and POLAR SMART.

* LA dwell time is defined as time from the Cryoablation Catheter introduced in the LA to the last time of Cryoablation Catheter exiting the LA.

Table 6.2-1 Overview of objectives and endpoints

OBJECTIVES	ENDPOINTS	JUSTIFICATION FOR ENDPOINTS
Primary		
To establish continued safety of the cryoablation System in Asian geographies	Event free rate of a composite of procedure and device study specific adverse events (acute: 7 days and chronic: 12 months follow-up)	Majority of the BSC POLARx™ system studies data were collected predominantly in North American and European populations, it will be necessary to collect systematic scientific evidence unique to Japan and South Korea to proactively capture the impact on medical outcome driven by socio-economic, healthcare and epidemiological differences

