Reasons for withdrawal include but are not limited to physician discretion, change in inclusion/exclusion status, subject choice to withdraw consent, lost to follow-up, or death. While study withdrawal is discouraged, subjects may withdraw from the study at any time, with or without reason, and without prejudice to further treatment. All applicable case report forms up to the point of subject withdrawal and a "End of Study" form must be completed.

Every effort should be made to obtain full information on any ongoing reportable adverse events up to the point of withdrawal. All open reportable adverse events should be closed or documented as chronic. Data collected up to the point of subject withdrawal may be used,

unless any local regulations apply. Additional data may no longer be collected after the point at which a subject has been withdrawn from the study or withdraws his/her consent, for whatever reason.

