11.1.1. Primary Safety and Effectiveness Endpoints

11.1.1.1. Statistical Methods

The 12-month (365-day) event/failure-free rates will be calculated using Kaplan-Meier methodology. Subjects who withdraw from the study prior to 12 months without experiencing an event will be censored on the date of withdrawal. The corresponding 2-sided 95% confidence limits will be calculated as the pointwise confidence limits using the log-log methodology.

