17.1. Reportable Events by investigational site to Boston Scientific

It is the responsibility of the investigator to assess and report to BSC any event which occurs in any of following categories:

- All Serious Adverse Events, including all events leading to death;
- All Thromboembolic Events;
- All Study Procedure Related AEs (index and repeat procedure);
- All Study Device-Related Adverse Events;
- All Study Related Device Deficiencies;
- Unanticipated Adverse Device Effects/Unanticipated Serious Adverse Device Effects previously not defined in the IFU;
- All BSC Commercialized Device-Related Adverse Events;

When possible, the medical diagnosis should be reported as the Event Term instead of individual symptoms.

If it is unclear whether or not an event fits one of the above categories, or if the event cannot be isolated from the device or procedure, it should be submitted as an adverse event and/or device deficiency.

Any reportable event, experienced by the study subject after informed consent, whether prior to, during or subsequent to the procedure, must be recorded in the eCRF.

Underlying diseases and chronic conditions are not reported as AEs unless there is an increase in severity or frequency during the course of the investigation. Death should not be recorded

as an AE, but should only be reflected as an outcome of one (1) specific SAE (see Table 17.2-1 for AE definitions).

Death should not be recorded as an SAE but should only be reflected as an outcome of one (1) specific SAE (see Table 17.2-1 for Safety definitions).

If the subject experiences a new arrhythmia between index procedure and end of study, and the investigator considers this adverse event to be procedure related, it needs to be reported.

The following clinical events will not be considered adverse events for this clinical study:

- Pre-existing diseases or conditions (including AF, AFL, AT) will not be reported as adverse events unless there has been a substantial increase in severity or frequency of the problem as compared to the subject's baseline which cannot be attributed to the expected progression of the disease or condition;
- A recurrence of an arrhythmia should be reported on the "AF recurrence" eCRF and should not be recorded as an adverse event, unless it meets seriousness criteria as per table 17.2-1;
- Pre-planned hospitalizations at time of enrollment or for a pre-existing condition;

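### A procedure- or device-related death after day 7 and discharge, with no listed component event, does not lower the 12-month primary safety rate

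*Combined protocol and SAP*

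**What the plan says.** Section 6.2.1 and the synopsis set the time point: "The primary safety endpoint will be evaluated by the safety event free rate at 12 months post-index procedure". The composite is restricted to procedure-related and device-related events and has two lists.

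- **Acute list.** "Acute primary safety endpoint events, events occurring up to 7 days post-index procedure or hospital discharge, whichever is later, include": eleven components, among them death, myocardial infarction, stroke and thromboembolism.
- **Chronic list.** "Chronic primary safety endpoint events, events occurring through 12 months post-index procedure, include": four components, namely atrio-oesophageal fistula, significant pulmonary vein stenosis, symptomatic pericardial effusion and persistent phrenic nerve injury. Death is not one of them.

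Table 6.2-1 repeats the split as "acute: 7 days and chronic: 12 months follow-up".

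The analysis is in section 11.1.1.1: "The 12-month (365-day) event/failure-free rates will be calculated using Kaplan-Meier methodology". Its censoring rule is: "Subjects who withdraw from the study prior to 12 months without experiencing an event will be censored on the date of withdrawal". Section 9.2 on withdrawal includes among its reasons "subject choice to withdraw consent, lost to follow-up, or death".

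On recording, section 17.1 says: "Death should not be recorded as an SAE but should only be reflected as an outcome of one (1) specific SAE". Section 17.4 (Table 17.4-1) and section 17.7 require every death to be reported within three calendar days.

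**The concern.** A reader of a 12-month safety rate will expect a death caused by the procedure or the device to lower it. Here that holds only up to day 7 or discharge, whichever is later. After that, a related death lowers the rate only if the subject also had one of the four chronic events, or had a listed acute event inside the window.

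Take a subject discharged on day 3 who has a procedure-related stroke on day 9 and dies of it on day 14. The stroke has onset after the acute window and is not a chronic component. The death is also after the window and not a chronic component. The subject leaves the risk set as a withdrawal. If no other subject had an event, the study would report a safety event-free rate of 100% despite a fatal complication.

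No section gives late related deaths a rule of their own, a competing-risk treatment or a sensitivity analysis.

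**Working it through.** The documents state no expected safety event rate, performance goal or precision target, so there is no planned figure to reproduce. The check compares the two ways of handling the same death.

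**Inputs from the documents.** Kaplan-Meier estimate at day 365 with two-sided 95% pointwise log-log limits (11.1.1.1). A minimum of 200 PVI-only subjects, and an overall ceiling of 400 (7.1). The main analyses use PVI-only subjects (11.2.1), so N=400 is an upper bound for the main set.

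**Assumptions, not in the documents.** 0, 4 or 8 acute events, all on day 1; 1 to 3 late related deaths with no listed component event; no other censoring.

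**Formulas.** With a acute events, the estimate before the death is (N − a)/N, with N − a subjects at risk.

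- Late death censored: the estimate stays at (N − a)/N.
- Late death counted: (N − a)/N × (1 − 1/(N − a)) = (N − a − 1)/N.
- Difference per death: 1/N, which is 1/200 = 0.50 points or 1/400 = 0.25 points.
- Limits: S^exp(±1.96 × se), where se = √G / |ln S| and G is the Greenwood sum of d/(r(r − d)), with d events among r at risk.

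**One case in full: N=200, a=4, one late death.**

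- Censored: S = 196/200 = 0.980. G = 4/(200 × 196) = 0.00010204, and √G = 0.010102. |ln 0.980| = 0.020203, so se = 0.500. The limits are 94.76% and 99.24%.
- Counted: S = 195/200 = 0.975. G = 4/(200 × 196) + 1/(196 × 195) = 0.00012821, and √G = 0.011323. |ln 0.975| = 0.025318, so se = 0.447. The limits are 94.10% and 98.95%.

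**Other cases.**

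| N | Acute events | Late related deaths | Deaths censored | Deaths counted |
|---|---|---|---|---|
| 200 | 0 | 1 | 100.00% | 99.50% (96.50 to 99.93) |
| 200 | 4 | 1 | 98.00% (94.76 to 99.24) | 97.50% (94.10 to 98.95) |
| 200 | 4 | 2 | 98.00% (94.76 to 99.24) | 97.00% (93.44 to 98.64) |
| 200 | 4 | 3 | 98.00% (94.76 to 99.24) | 96.50% (92.80 to 98.32) |
| 200 | 8 | 1 | 96.00% (92.16 to 97.98) | 95.50% (91.53 to 97.63) |
| 400 | 4 | 1 | 99.00% (97.36 to 99.62) | 98.75% (97.02 to 99.48) |

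For N=200 or N=400 with 4 acute events and one late death, the results are the same whether the death falls on day 8, 30, 200 or 364.

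**Two boundary checks at N=200 with 4 acute events.** A fistula on day 20 followed by death on day 25 gives 97.50%: that death is captured through the chronic component. A death censored on day 30 with another subject's chronic event on day 300 gives 97.497%, against 97.500% if the first subject had stayed event-free to day 365. The censored death only shrinks the risk set slightly.

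**The case against.** The strongest reply is that this is a design choice. The acute and chronic split is the same in the synopsis, section 6.2.1 and Table 6.2-1. Ten other components share the acute window with death. Nothing in the documents says that later deaths were meant to count. That stands, and it rules out calling this a contradiction or a computing error.

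Four stronger readings are tempting, and the documents do not support them.

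- **That the Kaplan-Meier rate is biased upward.** A late death is not an event of the endpoint as defined, so leaving it out does not bias the estimate of that endpoint. The estimate is too high only for a different quantity, one in which late related deaths count.
- **That every fatal complication after day 7 is missed.** Fatal fistula and fatal symptomatic pericardial effusion count through 12 months, so a symptomatic pericardial bleed on day 9 would count. A listed acute event inside the window counts even if the subject dies later, and so does a related death before a delayed discharge.
- **That the dead subject is carried as event-free to day 365.** The subject leaves the risk set at death. The estimate simply does not fall.
- **That section 17.1 lets the same death be counted or not at will.** It is a recording rule for adverse events. The window refers to when events occur, and for the component death that most naturally means the date of death. The rule is nevertheless not stated, and one sentence would settle it.

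It is also fair to say that deaths are not hidden, since all are reportable within three calendar days, and that no decision turns on the rate because section 11 plans no formal hypothesis tests. Both points limit the consequence. Neither puts a late related death into the primary rate.

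**Conclusion.** The point holds as a gap in what the endpoint captures. A related death after day 7 and after discharge, with no listed component event, is not a primary safety event and does not lower the 12-month safety event-free rate. The typical case is a fatal stroke, myocardial infarction or thromboembolism with onset after the acute window.

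The size is 0.50 points per such death at N=200 and 0.25 at N=400. In the fully worked case the interval is about 4.5 points wide (99.24 − 94.76 = 4.48), so one death moves the estimate by much less than its uncertainty. The weight of the point lies in the kind of event left out. The documents give no expected frequency for such deaths, so the counts used here are assumptions and the true number may be zero.

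The censoring step rests on reading section 9.2 together with section 11.1.1.1. No sentence says outright that deaths are censored, but no other rule in the plan applies to them.

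**What to change.** **Preferred.** Add to the chronic list in section 6.2.1 and in the synopsis: death related to the index procedure or study device, through 12 months.

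**Minimum alternative.** Leave the endpoint as it is, and pre-specify in section 11.1.1.1 a sensitivity analysis that counts these deaths as events, reported beside the primary rate.

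With either option:

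- State that the date of death is the event date. Collect it routinely, because section 17.7 asks for the narrative that contains it only when the sponsor requests it.
- State that only unrelated deaths are censored in the analysis that counts related ones.
- Report acute-window deaths on a separate line, so that the present component stays visible.

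**Cost.** Follow-up to 12 months, death reporting and the relatedness assessment in section 17.3 are already in place. The preferred option is a short protocol amendment, which section 14.3 makes subject to ethics approval before it takes effect. The event-free rate may come out slightly lower.
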